5.0 Study Intervention/Investigational Agent

Tonation and Breathing Techniques (TBT): consist of a combination of organic inhalation and controlled exhalation with tonation. This will be guided by a trained facilitator, and the entire exercise will take 20 minutes.

1. Guided relaxed breathing: the subjects are asked to be conscious of any tensing of muscles all along the respiratory system and guided to relax them.
2. Mindful breathing: the subjects are next asked to observe their breathing and its effects at different points in their body.
3. Patterned tonation: the subjects are asked to hold a tone at any frequency comfortable to them, followed by a slightly lower frequency, a slightly higher frequency and then again at their original frequency.
4. Nasal tonation: The subjects are asked to close one nostril, inhale gently through the other nostril, followed by slow exhalation with tonation. This is done for 5 repetitions. The process is repeated for the other nostril.
5. Pursed lip tonation: The subjects are asked to inhale gently through their nostrils, purse their lips (in the motion of sucking a straw or blowing a balloon) and then exhale through their mouth with tonation. This is done for 5 repetitions.

Music Driven Vocal Exercises (MDVE): The following Music Therapy procedure will be implemented by a trained facilitator, utilizing an accompanying instrument (ie, guitar or Autoharp) and moving stepwise up and down within a scale of 8 whole steps. The total length of the procedure is 20-25 minutes.

1. Subjects will be taught the following vocal exercises that they will sing 10x each in the following order
 - a. Ha-Ha-Ha (Do-Re-Do)
 - b. Hee-Hee-Hee-Hee (Do-Re-Do-Ti-Do)
 - c. Hoo-oo-oo-oo-oo-oo-oo-oo-oo (Do Re Mi Fa Sol Fa Mi Re Do)
2. Subjects will be taught the following melodic exercises that they will sing 10X and then speak 5X. The first session will consist of the first 3 phrases, each subsequent session will add the next phrase on the list.
 - a. Whose Hands Hold Hearts Harps and Hangers (Do-Re-Do-Fa-Re-Do-Ti-Do)
 - b. Peter Piper Picked a Peck of Pickled Peppers (Do-Re-Do-Ti-Do-Re-Do-Re-Mi-Re-Do-Do)
 - c. Awkward Alice Ate Apples At an Airport (Do-Mi-Sol-Mi-Mi-Fa-Mi-Re-Mi-Mi-Do)
 - d. Granny Grills Grits for Gorillas (Do-La-Ti-Do-Do-Re-Mi-Do)
 - e. Zealous Zebras in Zoot Suits (Do-Re-Mi-Re-Fa-Do-Do)

- f. William and Gabby Grow White Grapes in Gorgeous Wintry Gardens (Do-Mi-Re-La-La-Ti-Re-Do-Ti-Do-Re-Re-Do-Mi-Do)

6.0 Procedures Involved*

Patients who are referred for pulmonary rehabilitation for chronic lung disease and/or post-COVID19 therapy, who have had pulmonary function testing already will be approached. Pulmonary rehabilitation is an 8-week program (meeting 3 times per week for the 8 weeks). Pulmonary rehabilitation (PR) is standard of care for patients with chronic lung diseases and or post-COVID-19 therapy. Eligible study participants will be called prior to their introductory PR session to explain the research project, and those who are interested will be given full information and offer time to ask questions. We find this necessary for logistics, given many of our patients rely on scheduled transportation to/from PR and this will allow those who are interested in obtaining more information and to consent to the study to arrange for appropriate transportation. Informed consent will be done in person on an individual basis at their introductory PR session, with 1:1 discussion with the study staff and the patient.

As this is a pilot study to determine feasibility, and preliminary data (as no data are currently available for this patient population), we propose 16 participants in total, 4 in each arm of the study. Randomization will occur by random number generator (1-4 for each arm proposed).

Once informed consent is obtained, patients will be randomized to 4 arms of the study. Randomization will be performed using a random number generator.

- 1) Comparing TBT to normal breathing:
 - a. Of the 8 weeks of PR, first 4 weeks will be sessions of normal breathing exercises for 20 minutes, then subsequent 4 weeks will be with TBT intervention for 20 minutes.
 - b. Of the 8 weeks of PR, first 4 weeks will be with TBT intervention for 20 minutes, then next 4 weeks will be of sessions of normal breathing exercises for 20 minutes.
- 2) Comparing MDVE to normal breathing:
 - a. Of the 8 weeks of PR, first 4 weeks will be sessions of normal breathing exercises for 20 minutes, then subsequent 4 weeks will be with WT intervention for 20 minutes.
 - b. Of the 8 weeks of PR, first 4 weeks will be with MDVE intervention for 20 minutes, then next 4 weeks will be of sessions of normal breathing exercises for 20 minutes.

These interventions would be performed after usual PR time, when patients would be normally discharged home. Therefore, no additional monitoring is expected.

Pulmonary function testing is standard for all patients who receive PR – testing before and after PR is routine clinical course. We propose an additional PFT study at 4 weeks, as part of the research protocol (covered by the Department of Medicine funding)

In summary, the interventions for research purposes will include:

- 1) 20-minute sessions after PR for intervention (TBT or MDVE) or normal breathing for twice a week for the 8 weeks they are participating in PR.
- 2) PFT at end of week 4

Proposed subjective outcomes are routinely asked of PR patients, but will be collected at baseline, at 4 weeks (mid-way), and at 8 weeks (end) of PR.

Proposed objective outcomes:

- 1) For FEV1, FVC – these are routinely collected at baseline and at end of PR. We propose an additional PFT study at 4 weeks, covered by the DOM Faculty Development Fund.
- 2) For peak flow and NIF – these are procedures that ask for patient to breathe maximally for inspiration and expiration. They are not routine measures collected but are routine bedside measurements for pulmonary patients that can be collected for any person without any additional risk or cost.

Data will be obtained as following:

- 1) Routinely obtained information will be collected from EPIC into a REDCap database. This includes:
 - a. Patient demographics – name, MRN, DOB, sex, gender, race, ethnicity, height, weight, BMI,
 - b. Pulmonary history: reason for PR referral (routine collection); date of symptom onset; date of diagnosis of lung pathology; prior PFT findings – FEV1, FVC, peak flow, NIF.
 - c. PR questionnaire info: Borg dyspnea score at baseline and each visit (routine collection)

There are no plans for long-term follow-up.

7.0 Data and Specimen Banking*

Data will be obtained as following:

Routinely obtained information will be collected from EPIC into a REDCap database.

This includes:

- 7.1 Patient demographics – name, MRN, DOB, sex, gender, race, ethnicity, height, weight, BMI,
- 7.2 Pulmonary history: reason for PR referral (routine collection); date of symptom onset; date of diagnosis of lung pathology; prior PFT findings – FEV1, FVC, peak flow, NIF.
- 7.3 PR questionnaire info: Borg dyspnea score at baseline and each visit (routine collection)

Informed consent forms will be signed and scanned into patient charts (in the media manager). Physical consent forms will be retained in the PI's office, in a locked cabinet in the locked room for the required amount of time.

8.0 Sharing of Results with Subjects*

As this is a pilot project, no significant findings are expected from the study. For an individual, the results of repeat PFT testing done for research will be available to the patient in EPIC through MyChart.

9.0 Study Timelines*

An individual participants time in the study will be approximately 8 weeks.

Time 0 – Informed Consent signed.

Weeks 1-8 – normal Pulmonary Rehabilitation 3 times a week, with phonation intervention (TBT or MDVE) or silent breathing time.

On last session of week 4 and week 8: PFT's, NIF, VC, peak flows will be measured. Borg dyspnea scale will be collected.

We hope to collect 16 participants for this study by November 2022, and have primary analysis completed by December 2022 for submission to American Thoracic Society 2023 presentation.

10.0 Inclusion and Exclusion Criteria*

Inclusion:

- 1) Age 18 years and older
- 2) English-speaking and reading patient
- 3) Able to consent for study
- 4) Referred for pulmonary rehabilitation for chronic lung disease (including long COVID19 syndrome, COPD, ILD, PH)
- 5) Baseline Borg dyspnea score as moderate (score 3) or higher.
- 6) Has baseline pulmonary function testing available in electronic medical record.

Exclusion:

- 1) Cannot commit to staying an extra 30 min after Pulmonary Rehabilitation sessions for the study.

11.0 Vulnerable Populations*

This study does not include vulnerable populations.

12.0 Local Number of Subjects

Plan to recruit 16 participants for this study.

Anticipate needing to screen 40 participants for this study.

13.0 Recruitment Methods

Patients who are scheduled to start Pulmonary Rehabilitation will be called by one of the consenting investigators. The study will be described and any questions will be answered. The consent form will be sent to the patient to review in full. On the first day of Pulmonary Rehabilitation (PR), the patient will meet with a study investigator in a private room, and any further questions will be answered, and if patient is agreeable, will sign the consent form.

Source of participants will be all referred for Pulmonary Rehabilitation (patients are within the practice of the PI).

We will request partial HIPAA waiver to access patients' charts who are scheduled for Pulmonary Rehabilitation and assess inclusion and exclusion criteria and study eligibility. This will allow us to call patients and talk to them about their participation in this study, and answer questions prior to obtaining full informed consent.

A payment of \$10 by MetroHealth gift card will be given to the patient upon completion of 4 weeks of the research study / PR. An additional \$20 will be added to the participant's MetroHealth gift card on the last day of PR after completion of the study surveys and testing. This will be funded through the Pulmonary/CC Fellow MH Foundation fund.

14.0 Withdrawal of Subjects*

Participants of the study who miss 3 sessions of study intervention in the first 4 weeks of the PR will be notified that their enrollment in the study is at risk.

Participants who miss 4 sessions will be withdrawn from the study. They will be given written notification that their enrollment in the study is cancelled, and this will be put in the patient's electronic medical record, in the media manager.

Subjects will not have sufficient data collected to analyze, so the data will not be analyzed, and the participant will not count towards the expected enrollment number.

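### Randomised patients who miss four sessions leave both the analysis and the enrolment count, which hides non-attendance in a pilot meant to establish feasibility

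*Protocol*

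**What the plan says.** Section 6.0 sets the order of events: "Once informed consent is obtained, patients will be randomized to 4 arms of the study". Consent is signed at the introductory rehabilitation session, so no study session can have been missed before allocation. The target is 16 participants, 4 per arm (Sections 6.0 and 12.0).

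Section 14.0 has three parts:
- A warning goes to those who "miss 3 sessions of study intervention in the first 4 weeks of the PR".
- Then: "Participants who miss 4 sessions will be withdrawn from the study". This sentence gives no time window.
- Withdrawn participants are said to lack sufficient data, "so the data will not be analyzed, and the participant will not count towards the expected enrollment number".

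Section 2.0 makes feasibility hypothesis (a), and Section 3.0 makes it the step that must succeed before a larger trial is proposed. Section 4.0 lists only the Borg score and lung-function measures as endpoints. Nowhere does the protocol commit to reporting withdrawals or attendance. The only record of withdrawal it names is a written notice filed in the patient's chart.

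**The concern.** The intervention asks patients to stay on after rehabilitation for 20 to 25 minutes. Whether they do so is a central feasibility question, and Section 14.0 removes the patients who answer it with a no. No one among the counted 16 can have reached the missed-session limit, so a completion figure based on them says nothing about the share of randomised patients who did. A decision on the larger study needs that share.

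The analysed set is also selected on attendance after randomisation. That can disturb the comparison between arms, although the protocol gives nothing from which to derive the size or direction of the effect.

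**Working it through.** **The plan's own figures.** 4 arms × 4 = 16 participants. Section 6.0 schedules study sessions of the intervention or "normal breathing for twice a week for the 8 weeks they are participating in PR", so 2 × 8 = 16 sessions, 8 of them in weeks 1–4. Section 25.0 agrees: 2 × 8 × 16 × 0.5 h = 128 h. There is no power calculation and no miss rate.

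**Floors implied by the rule.** A counted patient has missed at most 3 sessions.
- Limit over all 16 sessions: at least 13/16 = 81% attended.
- Limit over the first 8 only: at least 5/8 = 63% in weeks 1–4, with no floor afterwards. Poor attendance in weeks 5–8 would then still show.

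**Share withdrawn.** Assume each session is missed with probability q, independently, with q = 10%, 20% or 30%. Then P = 1 − Pr(at most 3 misses in n sessions), and counting 16 takes 16/(1 − P) randomised on average.

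For q = 0.20:
- n = 8: P = 1 − (0.1678 + 0.3355 + 0.2936 + 0.1468) = 0.056, and 16/0.944 ≈ 17.
- n = 16: P = 1 − (0.0281 + 0.1126 + 0.2111 + 0.2463) = 0.402, and 16/0.598 ≈ 27.

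**Attendance read from the counted set.** This is 1 − E(misses | at most 3)/n.
- n = 16, q = 0.20: mean misses = (0.1126 + 2 × 0.2111 + 3 × 0.2463)/0.5981 = 2.13, so attendance reads 1 − 2.13/16 = 87% against a true 80%.
- n = 8, q = 0.20: mean misses = 1.44, so 82% in weeks 1–4. Over 16 sessions: (8 × 0.819 + 8 × 0.80)/16 = 81%.

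**Clustered misses.** The same quantities were computed with a beta-binomial, assuming a within-patient correlation of 0.3 (a + b = 0.7/0.3) and the same propensity in weeks 5–8.

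| | q = 10% | q = 20% | q = 30% |
|---|---|---|---|
| True attendance | 90% | 80% | 70% |
| **Limit over first 8 sessions** | | | |
| Withdrawn, independent | 0.5% | 5.6% | 19% |
| Randomised to count 16, independent | 16 | 17 | 20 |
| Attendance of counted, 16 sessions, independent | 90% | 81% | 73% |
| Withdrawn, clustered | 7% | 17% | 30% |
| Attendance of counted, 16 sessions, clustered | 94% | 89% | 84% |
| **Limit over all 16 sessions** | | | |
| Withdrawn, independent | 6.8% | 40% | 75% |
| Randomised to count 16, independent | 17 | 27 | 65 |
| Attendance of counted, independent | 91% | 87% | 85% |
| Withdrawn, clustered | 17% | 35% | 52% |
| Attendance of counted, clustered | 97% | 94% | 93% |

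**Session frequency.** Section 9.0 can be read as three study sessions a week, which would give 12 or 24 sessions. The same formula with independent misses then gives 2.6%, 21% and 51% withdrawn (n = 12), or 21%, 74% and 96% (n = 24).

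**Room for replacements.** Section 12.0 expects to screen 40, and Section 25.0 expects about 50% enrolment. If that 50% applies to those screened (an assumption), 40 × 0.5 = 20 enrol, leaving 4 replacements, or 1 − 16/20 = 20% withdrawn. With independent misses, P reaches 20% at q ≈ 15% (n = 16) or q ≈ 30% (n = 8).

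**Is the data reason sound?** Only in part. Borg is routine at baseline and every visit. On FEV1 and FVC, Section 6.0 says "these are routinely collected at baseline and at end of PR". The mid-point test is research only: "We propose an additional PFT study at 4 weeks, as part of the research protocol". A patient withdrawn before week 4 would therefore lack that test, and usually peak flow and NIF as well, so FEV1 and FVC could not separate the two periods. Borg scores would exist only for rehabilitation visits still attended. A patient withdrawn after week 4 would normally have the week-4 test. The enrolment denominator needs no outcome data at all.

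**The case against.** The strongest reply is that Section 14.0 governs when accrual is complete, not what is reported. No completion statistic is defined, so none is formally distorted. Withdrawal notices are filed in the chart and consents are logged in REDCap (Section 23.0), so both the withdrawals and the number enrolled can be recovered. This stands as far as it goes: the information is not lost. But the same sentence also bars analysis of these patients' data, and nothing in the protocol puts them back into any count.

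Second, the 4-miss sentence follows a warning tied to the first 4 weeks and may share that window. With independent misses, attendance over 16 sessions is then overstated by only 0 to 3 points. This is a fair reading, but the text does not settle it, and clustering raises the overstatement to 4, 9 and 14 points.

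Third, every miss rate is assumed, and Section 10.0 already excludes patients who cannot commit to the extra time, which may make the higher rates less likely. The screening comparison links two figures the protocol does not link, and Section 25.0 also speaks of 10 subjects initially. These points limit the magnitude. They do not touch the rule itself.

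Fourth, the protocol expects no significant results, and the reason about insufficient data is partly right. Both are accepted, and no claim is made about bias in the efficacy estimates.

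**Conclusion.** The rule is wrong as written and should be fixed. It makes the counted set depend on attendance after randomisation, in a study whose stated purpose includes feasibility. That conclusion needs no assumption: completion among the counted is 100% with respect to this rule, by construction.

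The practical size does rest on assumptions. With two sessions a week and miss rates of 10% to 30%, the share withdrawn and unseen in the counted set runs from 0.5% to 30% on the 8-session reading and from 6.8% to 75% on the 16-session reading, across independent and clustered misses. The overstatement of attendance may be small on the narrower reading. That withdrawn patients are replaced is an inference from not counting them toward a fixed target. The word itself is not used.

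**What to change.** Leave the attendance rule alone and change what happens to the data:
- Keep every randomised patient in the enrolment and feasibility denominator.
- Report withdrawals for missed sessions, and sessions attended, by arm over all randomised.
- Analyse available Borg and lung-function data in the assigned arm, as far as consent allows. Make the attenders-only analysis secondary.
- If four full crossovers per arm are wanted, add patients openly, without removing anyone randomised from the denominator.
- State the window of the 4-session limit, and reconcile the session frequency in Sections 6.0 and 25.0 with the wording of Section 9.0.

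The cost is protocol wording and possibly a check that consent covers routine chart data after withdrawal. No new measurements are needed, since Borg and the baseline and end-of-rehabilitation FEV1 and FVC are routine.

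The downside is a less favourable completion figure and fewer than 16 full completers unless patients are added. At an assumed 20% independent miss rate with no additions, 4 × 0.944 = 3.8 of 4 per arm would complete on the 8-session reading, and 4 × 0.598 = 2.4 of 4 on the 16-session reading.

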15.0 Risks to Subjects*

There are no foreseeable risks or hazards to the proposed interventions. There may be a discomfort in the phonation exercises, if persons have not done this before, but the participant is only asked to do what is tolerated. There is an inconvenience to the patient that they have to stay an extra 30 min after their usual PR session for the study intervention. They will be compensated \$30 total (\$10 at the beginning of the study, \$20 at the end of the study).

There are risks of loss of confidentiality in this study, as in any other study that identifies participants. No sensitive data will be collected, and the data will be stored in the secure REDCap system. Only de-identified data will be downloaded from REDCap for analysis purposes. This de-identified data will be stored in the PI's secure G: drive folder for research.

16.0 Potential Benefits to Subjects*

Individual participants may experience improved symptoms of dyspnea and pulmonary function. They may also enjoy the interaction with a trained music therapist.

Overall, the data from this study would inform a larger study that could show a novel way of improving pulmonary rehabilitation, and innovative ways to improve dyspnea symptoms and pulmonary function in patients with chronic respiratory illness.

17.0 Data Management* and Confidentiality

Descriptive analyses will be performed first on each of 4 categories. Chi-squared tests and ANOVA testing will be performed, although with low sample size, significance is not expected in these analyses. No power analysis will be performed, as this will be a pilot study.

Baseline data, including patient demographics, baseline pulmonary function test results, baseline Borg dyspnea score will be saved into a REDCap database. This database will only be accessible by study investigators. De-identified database will be downloaded for analysis, and this will be stored on the PI's G: drive research folder. Study records will be stored according to the MHS Record Retention Policy VII-4, which is minimum 4 years after study completion.

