2.0 Objectives*

The objective of this study is to determine whether breathing and vocalization exercises improve dyspnea in patients who are referred for pulmonary rehabilitation (PR).

The specific aims are to determine the following:

- 1) Do breathing and vocalization exercises improve subjective pulmonary symptoms and objective pulmonary function in patients referred for PR, compared to no intervention?
 - a. Specific outcomes include: subjective: Borg dyspnea score
 - b. Specific outcomes include: objective: Forced expiratory volume in 1 second (FEV1), forced vital capacity (FVC), Peak Flow, Negative Inspiratory Force (NIF), peak flow
- 2) Do breathing and vocalization exercises improve subjective pulmonary symptoms and objective pulmonary function, compared to calm normal breathing?
 - a. Specific outcomes include: subjective: Borg dyspnea score
 - b. Specific outcomes include: objective: FEV1, FVC, NIF, peak flow
- 3) Is there a difference between two different proposed techniques of breathing and vocalization exercise techniques to improve subjective pulmonary symptoms and objective pulmonary function?
 - a. Specific outcomes include: subjective: Borg dyspnea score
 - b. Specific outcomes include: objective: FEV1, FVC, NIF, peak flow

Our hypotheses are that breathing and vocalization techniques are a) feasible; b) can improve subjective and objective pulmonary outcomes; c) there is no significant difference between the two proposed techniques of breathing and vocalization techniques.

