25.0 Resources Available

Patients are enrolled in pulmonary rehabilitation each week – approximately 16 new patients per month. They are enrolled for an 8-week period. Based on prior research studies on the same patient population, we anticipate about 50% enrollment. This is a pilot project proposal, so we propose to recruit 10 subjects initially.

PI proposed about 2.5% of FTE to the research study. Fellows will have dedicated research time to enroll subjects and collect data. Music therapy consultants will spend about 30 min/patient session (2 sessions per week x 8 weeks x 16 participants = 128 hours) on the study. They have graciously offered to provide the music therapy intervention pro bono for this pilot study. Baseline and post-rehab PFT's are clinically routine. The research spirometry proposed at 4 weeks requires funding. Investigators have been awarded a DOM Faculty Development Grant to support this expense (\$150 per spirometry x 16 participants = \$2400). Additional funding is also provided by Arts in Health operating budget. Patient incentive MetroHealth gift cards will be funded by the MH Pulmonary/Critical Care Fellows Fund through the MH Foundation.

The study will be conducted in the Pulmonary Rehabilitation center, in Hamann 3rd floor in the H&V clinic. There are dedicated rooms for education that will be used for the intervention sessions. No additional equipment will be needed.

No medical or psychological support is anticipated as needed during these sessions. There is always a physician-on-call for pulmonary rehabilitation while patients are present. If the physician-on-call is notified about a patient who is enrolled in the current study and develops any complications during the intervention, the physician-on-call will notify the PI.

All study investigators and persons assisting with the research will be given the full study protocol. We will have regular meetings to determine study progress, review study procedures, and address any issues related to the proposed study.

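### The TBT versus MDVE comparison is between patients, 8 against 8, and section 17.0 names only ANOVA with no stated use of the stored baselines; on raw end-of-period values this loses precision if the baseline correlation exceeds about 0.3

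*Protocol*

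**What the plan says.** Section 2.0 of the protocol poses Aim 3 as a question: "Is there a difference between two different proposed techniques of breathing and vocalization exercise techniques". The outcomes are Borg, FEV1, FVC, NIF and peak flow.

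Section 6.0 sets the size: "we propose 16 participants in total, 4 in each arm of the study". Each arm pairs one technique with normal breathing in two four-week blocks, in one order or the other. One TBT arm, for example, reads "first 4 weeks will be with TBT intervention for 20 minutes, then next 4 weeks will be of sessions of normal breathing exercises for 20" (min). One MDVE arm calls its intervention WT, an undefined label. It stands under the MDVE heading, and I read it as MDVE.

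Section 10.0 admits a broad population: "Referred for pulmonary rehabilitation for chronic lung disease (including long COVID19 syndrome, COPD, ILD, PH"). It also requires a baseline Borg score of 3 or higher.

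The analysis is described in section 17.0 alone: descriptive summaries for four categories, then "Chi-squared tests and ANOVA testing will be performed, although with low sample size, significance is not expected in these analyses". It names no response (raw value, change or within-patient difference), no factors and no covariates. The next paragraph lists the data to be kept, including baseline pulmonary function results, and says that "baseline Borg dyspnea score will be saved into a REDCap database". Section 6.0 schedules the outcomes at baseline, week 4 and week 8.

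**The concern.** The crossover pairs each technique with normal breathing within a patient, which serves Aim 2. It does not make Aim 3 a within-patient comparison, because the patients who receive TBT are not those who receive MDVE. Patients with COPD, ILD, PH and long COVID can differ considerably in FEV1, FVC and breathlessness before the first session. With 8 per technique, the two groups may start apart by chance.

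An ANOVA of end-of-period values carries that starting difference into the TBT-MDVE estimate and leaves all the between-patient variation in its error term. The baseline that could reduce both is already in the database.

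Section 3.0 says a later, larger study will compare the two approaches. Section 2.0 expects no significant difference between them, and section 17.0 expects no significance at all. The useful product of Aim 3 is therefore an estimate with its interval, so the width of that interval is what is at stake.

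**Working it through.** **Inputs from the protocol.** Four arms of 4 (section 6.0): 4 x 4 = 16, which reproduces the stated total. Two arms per technique give 2 x 4 = 8 TBT and 8 MDVE patients. Within each technique, 4 patients have it in weeks 1-4 and 4 in weeks 5-8. No SD, effect size or power is given (section 17.0), so there is no power figure to reproduce.

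**Assumptions.** A two-sided 95% interval; results in units of the outcome SD; rho, the correlation between a measure's baseline and its later value, is not in the protocol and is varied. The correlation between the two end-of-period values is first taken as equal to rho.

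**Models compared**, each with technique and period as factors:

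1. Raw technique-period value: 16 - 3 = 13 residual degrees of freedom. Half-width = t(0.975, 13) x sqrt(2/8) = 2.1604 x 0.5 = 1.080 SD.
2. The same value with its own baseline as covariate: 12 degrees of freedom. Half-width = t(0.975, 12) x sqrt[(2/8)(1 - rho^2)(1 + 1/11)] = 2.1788 x 0.5 x 1.0445 x sqrt(1 - rho^2) = 1.138 x sqrt(1 - rho^2). The factor 1 + 1/11 is the expected cost of estimating the covariate slope.
3. Technique minus normal breathing within patient, then TBT against MDVE: variance 2(1 - rho), 13 degrees of freedom. Half-width = 1.080 x sqrt[2(1 - rho)].

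| rho | Raw | Own-baseline covariate | Change from raw | Within-patient difference |
|---|---|---|---|---|
| 0 | 1.080 | 1.138 | +5% | 1.528 |
| 0.3 | 1.080 | 1.085 | 0% | 1.278 |
| 0.5 | 1.080 | 0.985 | -9% | 1.080 |
| 0.7 | 1.080 | 0.813 | -25% | 0.837 |
| 0.8 | 1.080 | 0.683 | -37% | 0.683 |
| 0.9 | 1.080 | 0.496 | -54% | 0.483 |

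**Break-even.** Model 2 equals model 1 when 1.138 x sqrt(1 - rho^2) = 1.080, that is at rho = 0.31. Leaving the period factor out of both models gives 1.072 SD raw and a break-even of 0.30.

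**Sensitivity.**
- *Correlation that fades with time.* Under first-order autoregressive correlation with rho = 0.7 between adjacent visits, the simulated average half-widths are 0.82 for the within-patient difference, 0.89 for the baseline-adjusted value and 1.06 raw. There the difference does better.
- *Baseline added to the within-patient difference.* The simulated interval widens by about 5% (0.82 to 0.86 at rho 0.7).
- *Three baselines at once.* With Borg, FEV1 and FVC together and no period factor, break-even rises to a multiple correlation of about 0.52.
- *Smaller enrolment.* Section 25.0 says "This is a pilot project proposal, so we propose to recruit 10 subjects initially". With 10 patients, one covariate and no period factor, break-even is about 0.43.
- *Unequal groups.* The 8:8 split is the plan. If the random number draw is unrestricted, an exact 8:8 split has probability C(16,8)/2^16 = 12870/65536, about 20%.

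**The case against.** The strongest reply is that section 17.0 is silent rather than wrong. It does not exclude the baseline. Section 1.0 words its objectives as improvement, and outcomes are taken at baseline, week 4 and week 8, so an ANOVA of change or a repeated-measures ANOVA would fit the text and would use the baseline. The choice of covariates is often left to a statistical analysis plan, which is not at hand. A reader might infer that the plan rules out baseline adjustment; the text does not support that. What stands is that the protocol does name a method, that the method in its ordinary form has no covariate, and that no use of the stored baselines is stated.

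The second reply is that the comparison with raw values takes the weakest reading. The natural crossover quantity, technique minus normal breathing, gets nearly all the gain at rho of 0.7 or more and does slightly better at 0.9. This stands, and it limits the claim. But the difference only matches the raw analysis at rho 0.5 and is worse below that. Section 6.0 also states no washout, so in technique-first arms the normal-breathing value may still carry an effect of the technique. The technique-period value never follows another active technique.

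Third, rho is assumed throughout. The entry floor of 3 on Borg restricts its range and may lower rho for the primary outcome, possibly to where adjustment gains little. This stands.

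Last, the trial is a feasibility pilot that expects no significance, and no decision rule rests on the interval. This limits the stakes, although interval width still matters for the preliminary estimate.

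**Conclusion.** The point holds in conditional form. Aim 3 is a between-patient comparison of 8 against 8 as planned, in mixed lung disease, and the one model named for continuous outcomes has no stated use of the stored baselines. If it is run on raw end-of-period values, precision is lost whenever rho exceeds about 0.3: the half-width is 1.080 SD where 0.985, 0.813 or 0.496 SD was available at rho 0.5, 0.7 or 0.9. These figures assume 16 completed patients split 8:8, equal correlation between visits, and a rho that the protocol does not supply.

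Two stronger conclusions are tempting, and neither is supported. Precision is not shown to be lost under every reading of the ANOVA, since an analysis of within-patient differences would perform much like the covariance model at rho of 0.7 or more. Nor would adjustment remove imbalance in disease mix; it accounts for the one measured baseline that is entered. The consequence for this pilot is modest, but the correction uses data already collected.

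**What to change.** In section 17.0, for Aim 3, replace ANOVA with analysis of covariance on the technique-period value (week 4 or week 8, according to arm). Use technique and period as factors and the same measure's baseline as the only covariate, so one covariate per outcome. Apply it to Borg, FEV1 and FVC, and to NIF and peak flow where a pre-treatment value exists. Report the adjusted TBT-MDVE difference with its 95% interval.

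Do not enter several baselines together at this sample size. Do not add the normal-breathing-period value as a covariate, because in technique-first arms it is measured after the technique. Do not describe the adjustment as correcting for disease mix.

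The cost is one sentence and no new data. The statistical price is one degree of freedom, and an interval up to about 5% wider if rho is below about 0.3.
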